The epigenetic effect of salt intake will be investigated through a two-sample t-test to identify methylation sites with significant methylation level difference between treatment and placebo. At a minimum of 5X coverage and an average coverage of 30X, the SureSelect-MethSeq (SS-Methseq) platform captures between 2.6 and 2.3 million methylation sites. After thorough processing and QC of the methylation data, using the Bismark pipeline, samples and methylation sites that passed all QC filters will be considered for the analysis. Each methylation site will be treated as a continuous variable and salt intake will be treated as a nominal variable with two categories (treatment and placebo), in the t-test. In such analysis, the methylation sites are assumed to be independent and there is, hence, a high burden of multiple testing due to the millions of sites being tested. Therefore, a significance threshold of p-value  $< 9 \times 10^{-8}$  will be applied to control for false positive findings; this threshold was derived from empirical work based on the Illumina EPIC array which has a lower density than the SS-Methseq platform but includes carefully selected sites that span the whole genome. The estimated mean difference, p-value and 95% confidence interval of the t-test will be presented as the results.

After the transcriptome, epigenome and microbiome data have been considered separately in the analyses described above and to understand the links between gene expression and methylation, an ensemble technique such as Random Forests will be used to leverage the high dimensionality of the data (number of features >> number of observations) and identify the best combination of predictors of salt intake in the transcriptome and epigenome data. Subsequently, the OTUs identified in the microbiome data will be integrated to find out if microbiome information improves the prediction accuracy of the omics data. This will provide further insights into the interplay between the three domains (microbiome, transcriptome and epigenome).

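### The methylation cut-off of 9 × 10⁻⁸ is not derived from the number of sites tested; with independent sites and a valid within-person test, the chance of at least one false site is up to 19–21%

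*Combined protocol and SAP*

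**What the plan says.** Section 9.4.3 gives the epigenome analysis in one paragraph. The effect of salt on methylation "will be investigated through a two-sample t-test" at each site. The "platform captures between 2.6 and 2.3 million methylation sites", and "samples and methylation sites that passed all QC filters will be considered for the analysis"; the number expected to survive is not given. For the tests, "the methylation sites are assumed to be independent", which the plan recognises as a heavy multiplicity burden. It answers that burden with a fixed p < 9 × 10⁻⁸, which "will be applied to control for false positive findings". The plan discloses that the threshold comes from empirical work "based on the Illumina EPIC array which has a lower density than the SS-Methseq platform". It defends the choice on the ground that the array "includes carefully selected sites that span the whole genome".

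The other omics analyses are handled differently. Microbiome features (9.4.2) and RNA-seq genes (9.4.3) are both corrected by Benjamini-Hochberg at 0.05 over the features actually tested. Section 9.2 names paired t-tests for normally distributed data, and a linear mixed model with subject as a random effect whose listed outcomes include the epigenome.

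**The concern.** The paragraph states the size of its multiplicity problem and then uses a cut-off that does not depend on that size. Under its own premises (independent sites, millions of them), the number of tests determines how strict the per-site threshold must be, and the plan names no error rate that 9 × 10⁻⁸ is meant to deliver.

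Whole blood epigenome is a named secondary endpoint, and what will be reported for it is the set of sites passing this threshold. With 40 participants planned (9.2) or 28 enrolled (section 12, the data-transfer addendum), one or two chance sites could be presented as the epigenetic effect of salt. Under independence, methylation would also be held to a looser standard than the other two omics analyses: when no feature is truly affected, Benjamini-Hochberg at 0.05 limits the chance of any false call to 5%.

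**Working it through.** **Inputs**
- Per-site cut-off: 9 × 10⁻⁸ (9.4.3).
- Sites m: 2.3 to 2.6 million captured (9.4.3). The post-QC count is not given, so this is a ceiling.
- Dependence between sites: none, by the plan's assumption (9.4.3).
- Benchmark: 5%. The plan does not state it for methylation; it is taken here from the general 0.05 rule in 9.2 and the 0.05 level used for the other omics data.
- Participants: 40 planned (9.2), 28 enrolled (section 12); 34 is the dropout-adjusted size in 9.2.
- Within-person correlation ρ: 0.3 is given for pulse wave velocity (9.2), none for methylation. Values from 0 to 0.5 are assumed.

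**Step 1. Can 9 × 10⁻⁸ be reproduced?** No. The documents give neither an error rate nor an array site count from which to derive it. Bonferroni with the plan's own m gives 0.05 / 2,300,000 = 2.17 × 10⁻⁸ and 0.05 / 2,600,000 = 1.92 × 10⁻⁸. The stated cut-off is looser than these by factors of 4.1 and 4.7. Inverted, 0.05 / (9 × 10⁻⁸) ≈ 556,000 independent tests.

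**Step 2. False sites with valid, independent tests and no QC loss.** Expected number = m × 9 × 10⁻⁸. Chance of at least one = 1 − (1 − 9 × 10⁻⁸)^m.

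| m | Expected false sites | Chance of at least one |
|---|---|---|
| 2.3 million | 0.207 | 18.7% |
| 2.6 million | 0.234 | 20.9% |

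**Step 3. How far each condition matters.**

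*Correlated sites.* If the effective number of tests is a fraction of m:

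| Effective fraction | Chance of at least one (2.3 to 2.6 million) |
|---|---|
| 50% | 9.8% to 11.0% |
| 25% | 5.0% to 5.7% |
| 20% | 4.1% to 4.6% |

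*QC loss.* With independent sites, 2.0 million survivors give 16.5%, 1.5 million give 12.6%, 1.0 million give 8.6% and 0.56 million give 4.9%.

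*The unpaired test as written.* In a crossover, the mean difference has null variance 2σ²(1 − ρ)/n, but a two-sample t-test divides by a standard error built on about 2σ²/n. With ρ > 0 the statistic is too small, and this far out in the tail the effect is large. The true per-site error was found by averaging the normal tail over simulated pooled variances, with critical t on 2n − 2 degrees of freedom and one value per participant per treatment:

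| n | ρ | Per-site error | Chance of at least one (2.3 to 2.6 million) |
|---|---|---|---|
| 28 | 0.1 | 2.7 × 10⁻⁸ | 6.1% to 6.9% |
| 40 | 0.1 | 2.4 × 10⁻⁸ | 5.3% to 6.0% |
| 28 | 0.3 | 1.4 × 10⁻⁹ | 0.33% to 0.37% |
| 40 | 0.3 | 8.0 × 10⁻¹⁰ | 0.18% to 0.21% |

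At n = 34 the results lie between these. At ρ = 0.5 every figure is below 0.01%. At ρ = 0 the step 2 figures return, apart from simulation error.

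**Step 4. What Benjamini-Hochberg would do.** With k sites declared, the largest admissible p-value is 0.05k/m. At k = 1 this is 1.9 to 2.2 × 10⁻⁸; at k = 4, 7.7 to 8.7 × 10⁻⁸; at k = 5, 9.6 × 10⁻⁸ to 1.09 × 10⁻⁷. It is stricter than 9 × 10⁻⁸ up to four declared sites and looser from five on.

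**The case against.** A reader might infer that the trial as written carries a chance of a false methylation site about four times an intended 5%. The documents do not support that, for four reasons.

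- **No 5% family-wise target is set for methylation.** The 0.05 in 9.2 is a general per-test rule, and the other omics analyses control a false discovery rate. This stands: 5% is a benchmark brought to the plan. The missing target is itself part of the problem.
- **The cut-off is empirical, the density mismatch is disclosed, and a reason is given.** The cited work may already allow for correlated sites, which cannot be judged from the documents. Nor do they give the array's site count, so 556,000 is only what 9 × 10⁻⁸ implies at 5% and not the array's size. What does not stand is the defence by genome-wide coverage: coverage does not show that the additional sites add no further tests. A return to 5% needs an effective count of about 21–24% of the captured sites (556,000 / 2.6 million and 556,000 / 2.3 million), and nothing in the plan supports that.
- **The tested count is unknown.** This also stands. However, the captured count is already quoted at a minimum read depth, and QC would have to remove roughly three quarters or more of the sites to bring 9 × 10⁻⁸ to 5%.
- **The two-sample t-test is conservative on crossover pairs.** This is the strongest point, and it stands for the test as written. It is not error control, though: the protection comes from ignoring the pairing, its size depends on an unknown correlation, and it costs power. It disappears once the paired or mixed-model analysis of 9.2 is used.

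**Conclusion.** The point holds in conditional form. The threshold does not follow from the plan's own premises, and the plan states no error rate for it to meet. With independent sites, little QC loss and a valid within-person test, 0.21–0.23 false sites are expected and the chance of at least one is up to 19–21%, against about 2 × 10⁻⁸ needed for 5%. That is close to an upper limit. Correlation between sites and QC loss lower it by amounts that the documents do not give. The unpaired test as written lowers it to about 5–7% at ρ = 0.1 and under 0.5% at ρ = 0.3. The issue concerns one secondary endpoint and should be corrected before the methylation data are analysed; it does not touch the primary endpoints.

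**What to change.** In 9.4.3, replace the fixed 9 × 10⁻⁸ with Benjamini-Hochberg FDR ≤ 0.05 over the methylation sites that pass QC, and report that number. Apply it to p-values from the within-person analysis already named in 9.2 (paired t-test or mixed model), in place of the two-sample t-test. This matches the RNA-seq and microbiome analyses and adjusts automatically for any QC loss.

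If family-wise control is preferred, say so and use 0.05 divided by the post-QC site count. The two options are not interchangeable, so one should be chosen in advance.

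The cost is a few words of text and no new data. The family-wise option drops sites with p between about 2 × 10⁻⁸ and 9 × 10⁻⁸ if nearly all captured sites survive QC. The FDR option is stricter than now when few sites are declared but, at that count, looser once about five or more are. It then controls the expected proportion of false sites among those declared, not the chance of any false site, and the report should say so.

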**4.2 SCIENTIFIC RATIONALE FOR STUDY DESIGN**

The study is testing the hypothesis that a modest increase in dietary sodium intake is sufficient to change the gut microbiome and trigger alterations in the blood transcriptome that may mediate the resultant in the well described salt-sensitive changes in vascular function, epigenome, transcriptome and blood pressure observed in African Americans. The study design as a randomized, double-blind, placebo-control cross-over design enables each participant to serve as her/his own control in response to the dietary salt intervention. The cross-over design allows for an intervening ‘wash-out’ period to ensure that the participant’s diet and sodium homeostasis returns to baseline. The design’s use of each participant as her/his own control reduces the impact of inter-individual variability in the basal dietary habits and microbiome; and optimizes statistical power to detect differences in baseline blood transcriptome gene expression profiles and gut microbiome in response to the dietary intervention. Our previous studies of the human transcriptome indicate that the current design is very robust to detect changes in gene expression by DNA methylation, RNA-seq and vascular function. The randomization ensures that the sequence order of the intervention (placebo vs salt tablets) is due to chance and avoids a systematic ‘contamination’ or carryover effect of the active treatment. The double-blind administration of tasteless capsules ensures that neither the participant or research staff are aware that there could be an increased ingestion of dietary salt. The dose of sodium chloride in the capsule has previously been shown to affect biomarkers sensitive to salt balance such as measures of the renin-angiotensin-aldosterone system and blood pressure. The daily dose of sodium chloride tablets given in the protocol falls well within the wide variance of ‘normal’,

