### **9.2 SAMPLE SIZE DETERMINATION**

Data will be tested for normality using the Shapiro-Wilk test. Continuous variables will be described as mean  $\pm$  standard deviation (SD) if normally distributed. Variables with skewed distribution (i.e. aldosterone, BNP, etc.) were logarithmically transformed prior to analyses and are presented as median and interquartile range (IQR). Categorical variables will be expressed as numbers (percentages).

When data are normally distributed, comparisons between the treatment (sodium intake) and control (placebo) groups will be made using paired Student's t-tests, and when data are non-

[figure not shown]
normally distributed, the Mann-Whitney U test will be employed. Chi-square test will be used for categorical variables. Tests for sodium intake effect on the primary outcomes without correction for period effect will be done using Mann-Whitney test on the differences. Tests for period effect will be assessed using two-sample Wilcoxon tests on the differences between treatment groups, and tests for carry-over effect will be assessed by a two-sample Mann-Whitney test on the averages in the two treatment periods. Correlations were determined with Pearson's correlation coefficient.

Additionally, we will evaluate the effects of sodium intake on changes in blood pressure, 24-hr ambulatory blood pressure monitoring (ABPM), biochemical markers, vascular functions, and specific transcriptome and epigenome by using a linear mixed model, with subject as a random effect, thereby accounting for the period, sequence, and carryover effects and to model the various sources of intra-individual and inter-individual variability. All statistical tests will be two-sided and P values  $<0.05$  will be regarded as significant. Statistical analyses will be carried out using SAS software (SAS Institute, Inc., Cary, NC, USA).

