The output of the pipelines are count data which are discrete, not continuous, and include only positive values. The counts,  $C_{ij}$ , are the observed number of microbes for the  $i^{th}$  sample and  $j^{th}$  feature where the features are the OTUs or microbial taxa. The data are normalized because library sizes (total counts for each sample, across all features) often have a large magnitude difference, which can cause a bias. The data are right skewed with, usually, a large number of data points having the value 0. Such data follows a Poisson distribution and therefore a Poisson regression model type (e.g. negative binomial model) will be used to investigate the relationship between microbiome and salt intake. For each feature, a model will be fitted with the feature as outcome and salt intake (a binary variable with two categories: treatment and placebo) as covariate. The differential count (fold change difference) between treatment and placebo will be estimated for each feature (OTU). To adjust for the multiple testing of several OTUs, a false discovery rate penalty will be applied and only fold changes with an adjusted p-value (Benjamini-Hochberg multiple test correction) smaller or equal to 0.05 will be considered statistically significant.

The analysis describes above using a Poisson regression model assumes the features (OTUs) are independent but it has been shown that microbial communities do interact in such way that changes in one feature affect another feature. However, the number of interactions can be large due to the number of features, and not easily fitted in a conventional regression model. Therefore, a machine learning algorithm (Random Forest or Neural Network) will be used to investigate the combined response of the features to salt intake. These algorithms can incorporate multiple and complex interactions between features without making an assumption about their distribution. The features will be used as predictor variables to predict salt intake (a binary variable with two categories: treatment and placebo). The results will be presented as the area under the curve (AUC) of a receiver operating curve (ROC) that reflect how well the features can predict treatment and placebo. Because these ensemble techniques do not assume the predictors

variable (OTUs) are independent, no multiple testing penalty is required but rather cross-validation will be undertaken.

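### The step meant to show links between methylation, gene expression and microbiome only predicts salt versus placebo, and a gain in prediction accuracy does not track whether domains are linked

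*Combined protocol and SAP*

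**What the plan says.** The last paragraph of section 9.4.3 describes an integrative step that follows the separate analyses of each domain. Its purpose is stated as "to understand the links between gene expression and methylation, an ensemble technique such as Random Forests will be used". The model is to "identify the best combination of predictors of salt intake in the transcriptome and epigenome data". OTUs are then added "to find out if microbiome information improves the prediction accuracy of the omics data". The paragraph concludes: "This will provide further insights into the interplay between the three domains (microbiome, transcriptome and epigenome)".

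Section 9.4.2 names a performance measure for the microbiome-only classifier: "The results will be presented as the area under the curve (AUC) of a receiver operating curve (ROC)". Section 9.4.3 speaks only of accuracy.

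Elsewhere the plan has one general sentence on association, in section 9.2, which names no variables: "Correlations were determined with Pearson's correlation coefficient". Section 9.4.9 rules out exploratory analyses. Section 4.2 gives the scientific rationale: a modest sodium increase is "sufficient to change the gut microbiome and trigger alterations in the blood transcriptome that may mediate the resultant" changes in vascular function, blood pressure and the molecular measures. Section 2.1 also speaks of microbiome change occurring in association with changes in the other measures.

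**The concern.** The question concerns how the domains relate to one another. The analysis has salt as its outcome throughout and the domains only as predictors. Selecting the features that jointly separate salt from placebo does not show whether a methylation change goes with an expression change in the same person. An accuracy increment from OTUs does not show whether microbiome change goes with change in the blood measures.

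This does not depend on how the classifier is validated. Perfect cross-validation would give an honest estimate of how well salt can be predicted, which is a different quantity. If the plan is followed as written, a stated question goes unanswered, and a figure that says nothing about links may be reported under the label of interplay.

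**Working it through.** **Plan's own figure.** There is none to reproduce. The plan gives no effect size, correlation or power for this step, so the values below are assumptions shown over a range.

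**1. Aim against output (section 9.4.3).**
- Expression and methylation: the aim is their links; the output is a set of predictors of salt.
- Three domains: the aim is their interplay; the output is a change in accuracy when OTUs are added.
- Neither output is a measure of association between domains. The unspecific Pearson sentence in 9.2 does not supply one.

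**2. Does accuracy gain track linkage?** Take one score per domain, each with SD 1 within condition. Salt shifts the score already in the model by d1 and the added score by d2. Their within-condition correlation is r. For the best joint classifier:

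D² = (d1² + d2² − 2·r·d1·d2) / (1 − r²), and AUC = Φ(√(D²/2)).

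With d1 = 1, the first domain alone gives Φ(√0.5) = 0.760.

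| d2 | r | D² | Joint AUC | Gain |
|---|---|---|---|---|
| 1 | 0 | 2.000 | 0.841 | +0.081 |
| 1 | 0.6 | 1.250 | 0.785 | +0.025 |
| 1 | 0.9 | 1.053 | 0.766 | +0.006 |
| 1 | −0.6 | 5.000 | 0.943 | +0.183 |
| 0.5 | 0 | 1.250 | 0.785 | +0.025 |
| 0.5 | 0.5 | 1.000 | 0.760 | 0.000 |
| 0.5 | 0.9 | 1.842 | 0.831 | +0.071 |
| 0 | 0 | 1.000 | 0.760 | 0.000 |
| 0 | 0.9 | 5.263 | 0.948 | +0.187 |

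A gain of +0.025 arises from unlinked domains (d2 = 0.5, r = 0) and equally from linked ones (d2 = 1, r = 0.6). A gain of 0.000 arises from unlinked domains (d2 = 0, r = 0) and from linked ones (d2 = 0.5, r = 0.5). Depending on d2 and the sign of r, a link can lower or raise the gain.

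**3. Order of entry.** Suppose salt acts on A and A alone drives B, so that A shifts by d, B shifts by r·d, and their correlation is r.
- Adding B (downstream) to A: D² = (d² + r²d² − 2r²d²)/(1 − r²) = d². The gain is exactly 0 for any r below 1.
- Adding A (upstream) to B: D² rises from r²d² to d². Take d = 0.667, the ratio 0.6/0.9 from the pulse wave velocity assumptions in section 9.2, used only as an illustrative size. The AUC goes from 0.593 to 0.681 at r = 0.5 (+0.088), from 0.647 to 0.681 at r = 0.8 (+0.034), and from 0.664 to 0.681 at r = 0.9 (+0.017). With the same shifts and no link, the gains at the first two would be +0.108 and +0.080.

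Section 9.4.3 enters the blood measures first and the OTUs last. If OTUs were upstream of the transcriptome, the second case would apply and the gain would not be zero.

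**4. Power of a direct test.** The addendum on data transfer reports 28 participants enrolled. By Fisher's z, power for correlation ρ is about Φ(atanh(ρ)·√(n − 3) − z), where z is the two-sided critical value.
- ρ = 0.5, n = 28: atanh(0.5)·√25 = 0.549 × 5 = 2.747. At 0.05, Φ(2.747 − 1.960) = 0.78, or about 0.80 without the normal approximation.
- At an assumed threshold of 0.0001, Φ(2.747 − 3.891) = 0.13.
- For 80% power at 0.0001: tanh((3.891 + 0.842)/5) = 0.74. At 0.00001: tanh((4.417 + 0.842)/5) = 0.78.
- If all 40 planned participants were analysable, the first of these would be tanh(4.733/√37) = 0.65.

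**The case against.** **Importance.** Links between domains are not among the listed objectives or endpoints (section 3) or the statistical hypotheses (section 9.1). The fifth hypothesis in 9.1, a blood epigenome/transcriptome signature of treatment, is reasonably served by finding the best joint predictors of salt. No primary or secondary estimate depends on this step. This stands and limits the weight of the point. It does not remove it, because 9.4.3 states the aim itself.

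**Stronger readings that a reader might infer.** Four go beyond the documents.
- That accuracy gain is inverted, largest when domains are unrelated. This holds for similar salt effects with non-negative correlation, but the table shows larger gains for linked domains in other cases. The measure is uninformative about links; it does not point the wrong way.
- That OTUs would add nothing if the study's own mechanism were true. Zero gain needs the downstream domain to be added last, whereas the plan adds OTUs last. Nor does section 4.2 clearly state a chain from OTUs to transcriptome: its sentence can equally be read as two parallel effects of sodium, followed by mediation of the vascular and pressure response.
- That methylation would be judged by an accuracy increment. That criterion is written only for OTUs.
- That the sponsor would read a null gain as no link. The plan promises further insight and gives no rule for interpreting the result.

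**Power of the alternative.** A direct test over many pairs will detect only strong links. This also stands. A low-powered test of the right quantity is still preferable to an accuracy figure that does not measure it.

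**Conclusion.** The concern holds as a mismatch between aim and method. Section 9.4.3 asks about links between domains and specifies only prediction of salt, and nothing else in the plan supplies a cross-domain analysis. Gain in accuracy is not a usable proxy: in the cases worked, linked domains give AUC gains from 0.000 to +0.187 and unlinked ones from 0.000 to +0.081, with some identical values in both groups.

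These sizes rest on assumed shifts and correlations and on a two-score normal model with the best possible classifier. They show what can happen, not what this trial will find. The conclusion that one gain can come from linked or unlinked domains does not need any particular value. The point concerns a secondary, integrative step and leaves the primary and main secondary analyses untouched.

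**What to change.** In section 9.4.3, add a direct analysis for the question on links:
- For each gene, correlate participants' salt-minus-placebo change in expression with their salt-minus-placebo change in methylation at sites within a window around the gene that is fixed in advance.
- Do the same for OTU change against expression change.
- Adjust for sequence, because a period effect enters the salt-minus-placebo difference with opposite sign in the two sequences and could otherwise create a correlation.
- Use permutation P-values, with Benjamini-Hochberg applied over the pairs tested.

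Keep the Random Forest as a description of how well salt can be predicted. State that a gain in accuracy, or none, is not evidence for or against a link.

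The cost is protocol wording and additional analysis; Table 2 already schedules blood, urine and microbiome samples at all four visits. The protocol should say openly that, with about 28 participants, only strong links will survive correction for multiple testing, and that 80% power at a correlation of 0.5 applies to a single pair at 0.05. A correlation of changes would show association, not which domain drives the other.
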